9. ADVERSE EVENT (AE) AND SERIOUS ADVERSE EVENT REPORTING (SAE)

Adverse events will be recorded for subjects starting at the time of signing the Informed Consent and their discontinuation within the study. All AEs will be recorded on an ongoing paper log, which will be reviewed by each site leader and forwarded to the team leader at London site, who will determine both the intensity of the event and the relationship of the event to study procedures. Based on the outcome it will be up to the team leader to medically determine if it is justified for the participant to continue in the study or terminate their participation.

SAEs will be recorded on a paper log, starting at the time of signing the Informed Consent and up to the end of their participation within the study. SAEs which are classified as unanticipated will be reported to local REBs. An SAE is defined as any incident that is unexpected, and related or possibly related to participation in the research study. SAEs will be reviewed and monitored by each site team leader until resolved.

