6. STUDY PROCESS

6.1 INTERVENTIONS

All participants will complete three (3) group training sessions per week (total 20 weeks), under the supervision of trainers. Each session will last approximately 90 minutes and will be comprised of 30 minutes cognitive training (CT) or control cognitive training (cCT) followed by approximately 60 minutes of combined aerobic and progressive strengthening exercise (E) or control tone-stretching exercise (cE) and. All participants will receive a vitamin D (tablet 10,000 IU) or placebo three times per week.

Within each small group of up to eight individuals, participants follow the program tailored to their individual functioning level, with constant monitoring by the trainers. Participants are expected to attend all training sessions and research staff will strongly encourage them to do so. Each training group will have 1-2 trainers present each session to ensure a ratio of one (1) trainer per four (4) participants. To

avoid potential imbalances in exposure time, control interventions for exercise and cognitive training will have the same duration.

Throughout the 12 month trial, participants will be provided with falls calendars, in which they will record any falls that have occurred, and they will be asked to bring them at the training sessions. At the completion of the 20-week intervention, participants are not given ongoing access to the training. During follow-up, participants will be called three months after their completion of the intervention to track incidence of falls, adverse outcomes, such as emergency room visits and change of medications; physical activity will be also be tracked using the Physical Activity Scale for the Elderly (PASE). Following assessments at 6 and 12 months, participants will receive a compensation of \$50 for their participation for a total of \$100.

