9.2 RESCUE MEDICATION AND RISK MANAGEMENT

Higher doses of Vitamin D may lead to hypervitaminosis D manifested by hypercalcemia and its sequelae. Treatment of acute or chronic intoxication includes withdrawal of Vitamin D3 and any calcium supplements, maintenance of a low calcium diet and if needed corticosteroids or calcuic diuretics, such as furosemide and ethacrynic acid to decrease serum calcium concentrations. All participants will be monitored by site physicians and trained staff should any adverse events arise participants will have access to a phone number and e-mail address provided on the copy of their signed consent form. They will be informed to use these contacts to inform the Principal Investigator about concerns that may be associated with treatment received in each site.

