9.3 PREMATURE WITHDRAWAL/DISCONTINUATION CRITERIA

Participants may be withdrawn or be discontinued from the study for any of the following reasons:

1. At the participant's request (withdrawal of consent)
2. At the discretion of the investigator, if deemed appropriate, for any reason
3. If an intolerable or life threatening adverse event occurs

Or if any of the following develop:

4. renal dysfunction
5. dementia
6. severe depression/anxiety/schizophrenia
7. hypercalcaemia and/or hypermagnesemia

Participant data collected to the date of discontinuation or withdrawal will be included in the analysis.

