10. ETHICAL CONSIDERATIONS

This study will be conducted in compliance with the outlined protocol, International Conference on Harmonization Good Clinical Practice (ICH-GCP), and all applicable regulatory requirements.

All relevant documents for this study will be submitted to the appropriate Research Ethics Board (REB) for review. Written approval from the REB must be obtained prior to entering and testing participants within this study. The REB will be notified of any protocol amendments regarding new study procedures which may occur during the course of the study. Written approval from the REB on these amendments must be received prior to implementation of any new procedures.

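### The SAE definition in Section 9 has no seriousness criterion and contradicts the ethics-board reporting sentence beside it, so serious events that are expected or unrelated are not classed as SAEs

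*Combined protocol and SAP*

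**What the plan says.** Protocol Section 9 sets out two streams.

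- **AEs.** "All AEs will be recorded on an ongoing paper log, which will be reviewed by each site leader". The log is then forwarded to the team leader at the London site, "who will determine both the intensity of the event and the relationship of the event to study procedures". Recording starts at consent.
- **SAEs.** These go on a paper log, also from consent, and each site team leader follows them until they resolve. The reporting rule is "SAEs which are classified as unanticipated will be reported to local REBs". The definition comes directly after it: "An SAE is defined as any incident that is unexpected, and related or possibly related to participation in the research study".

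No other section supplies a seriousness criterion. The nearest wording is a withdrawal reason in Section 9.3, "If an intolerable or life threatening adverse event occurs", which is not tied to SAE status. The SAP contains no SAE definition and describes no AE or SAE analysis. Protocol Section 8 states that the study raises no safety issues.

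**The concern.** Seriousness, expectedness and relatedness are three separate properties of an event. The definition uses the last two to stand for the first. The category labelled serious then depends on two judgements about cause and foreseeability, and on nothing about what happened to the participant.

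Two things are at stake. The first is follow-up: monitoring to resolution and REB reporting are attached to SAE status. The second is the meaning of any SAE figure the trial reports, since it would mix minor events in and leave serious ones out. Five sites review SAEs locally, so a definition at odds with its own label also invites inconsistent classification.

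**Working it through.** No arithmetic on rates or power applies. The check is a logical one on the text.

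**Step 1. Apply the definition to every type of event.** Each event is serious or minor, expected or unexpected, and related (or possibly related) or unrelated, giving 2 × 2 × 2 = 8 types.

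| Seriousness | Expectedness | Relatedness | SAE under Section 9? | SAE if defined by seriousness? |
|---|---|---|---|---|
| Serious | Unexpected | Related or possibly | Yes | Yes |
| Serious | Unexpected | Unrelated | No | Yes |
| Serious | Expected | Related or possibly | No | Yes |
| Serious | Expected | Unrelated | No | Yes |
| Minor | Unexpected | Related or possibly | Yes | No |
| Minor | Unexpected | Unrelated | No | No |
| Minor | Expected | Related or possibly | No | No |
| Minor | Expected | Unrelated | No | No |

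Three of the four serious types are left out and one of the four minor types is let in, so 3 + 1 = 4 of the 8 types are misclassified. This counts types of event, not events.

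**Step 2. Set the definition beside the REB sentence.** Under the definition, SAEs are the events that are unexpected and at least possibly related. Selecting the unanticipated ones from that set returns the whole set, so the qualifier does no work. If the qualifier is meant to do work, some SAEs must be anticipated, and the definition says none can be. Both sentences cannot stand as intended.

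**Step 3. Look for a criterion elsewhere.** The AE log carries intensity and relationship. Seriousness and expectedness are not listed. Intensity grades how severe an event is and does not enter the SAE definition. The telephone call three months after the intervention (Section 6.1) asks about "adverse outcomes, such as emergency room visits and change of medications", and the resource-use questionnaire (Section 7.6.9) asks about hospital admissions at Visits 2 and 3. Neither is linked to SAE status.

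**Step 4. Try it on a harm the protocol discusses.** Section 9.2 says "Higher doses of Vitamin D may lead to hypervitaminosis D manifested by hypercalcemia and its sequelae". Section 9.1 raises hypercalcaemia again under digoxin and thiazide diuretics, and Section 9.3 makes it a withdrawal criterion. A site could reasonably call such an event expected. If it did, even a serious case would fall outside the SAE definition.

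**The case against.** The strongest reply is that this is a drafting slip with limited reach. The definition follows straight after the REB sentence and may be a misplaced description of the events that must be reported to REBs. For serious events, the text already sends the unexpected and possibly related ones to the REBs, which is the set that should go. That much is fair. The slip still governs which events are labelled SAEs and followed to resolution, so the reply limits the point without removing it.

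Four stronger readings are tempting and should be resisted.

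- *A reader might infer that serious expected or unrelated events go unrecorded.* They do not. Section 9 puts all AEs on the log, with intensity and relationship. What is missing is SAE classification and what follows from it.
- *A reader might infer that a planned comparison of SAEs by arm would be biased.* Neither document plans one. The consequence holds for any SAE count that is reported.
- *A reader might infer that hypercalcaemia is excluded outright.* Section 9.2 ties it to higher doses and does not list it as expected, and Section 6.1.3 claims a 9-fold weekly safety margin for the trial's regimen. On that rationale a site could equally call it unexpected. The text leaves it open.
- *A reader might put a number on the hospital admissions left out.* The documents give no admission rate and no share judged unrelated, so any such number would rest on outside assumptions.

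Section 10 commits the trial to ICH-GCP. The documents do not reproduce that guideline's definition, so no weight is placed on it here.

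**Conclusion.** Wrong as written. The only SAE definition omits seriousness and is inconsistent with the sentence next to it. Applied literally, it misclassifies serious events that are expected or unrelated, and counts minor events that are unexpected and possibly related. Any SAE total from the trial would not measure serious harm.

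The reach is safety classification, follow-up and reporting. The number of events affected cannot be derived from the documents. Sample size, power and the primary efficacy analysis are not affected.

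The conclusion assumes that sites apply the definition as stated. Sites that read the word serious in its ordinary sense would misclassify less, but the protocol gives them no criterion to apply uniformly.

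**What to change.** 1. Redefine an SAE in Section 9 by seriousness of outcome. The documents contain no list of criteria, so the sponsor must write one (for example death, threat to life, hospital admission or a prolonged stay, lasting disability, or another medically important event).
2. Record seriousness, expectedness and relatedness as separate attributes. Relationship is already determined for logged AEs; seriousness and expectedness need adding.
3. Reword the REB sentence so that reporting covers SAEs that are both unexpected and related or possibly related. This keeps the apparent intent and removes the contradiction.
4. The SAP is marked final and dated September 2022, so events may already be logged. If so, reclassify all AE log entries by seriousness, blinded to arm, before safety is reported, and state in the report that this was done.

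The cost is revised wording, additions to the log, and somewhat more SAE paperwork for serious events judged unrelated. Retrospective reclassification also means re-reading the log, and it can only be as good as the detail recorded there.

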9.1 CONCOMITANT MEDICATIONS

Antacids (Magnesium-containing): Hypermagnesemia may develop when these agents are used concurrently with Vitamin D, particularly in patients with chronic renal failure.

Anticonvulsants (Phenytoin, Phenobarbital): Decreased Vitamin D effects may occur when certain anticonvulsants are administered, as they may induce hepatic microsomal enzymes and accelerate the conversion of Vitamin D to inactive metabolites.

Cholestyramine, Colestipol, Mineral Oil: Intestinal absorption of Vitamin D may be impaired. Patients on cholestyramine or colestipol should be advised to allow as much time as possible between the ingestion of these drugs and Vitamin D.

Digoxin: Vitamin D should be used with caution in patients on digoxin as hypercalcemia (which may result with Vitamin D use) may precipitate cardiac arrhythmias.

Thiazide diuretics: There is an increased risk of hypercalcaemia if vitamin D is coadministered with thiazide diuretics and calcium. Plasma-calcium concentrations should be monitored in patients receiving the drugs concurrently (Source: Martindale).

Different Vitamin D analogues should be administered concurrently.

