3. DESIGN

The **SYNERGIC TRIAL** (SYNchronizing Exercises, and Remedies in GaIt and Cognition) is a Randomized, modified factorial design with parallel-groups (five arms), and double-blind study **evaluating the cognitive effect of multimodal exercises (as a main intervention) combined with and without cognitive training and vitamin D**. This is achieved using 4 arms (1 to 4) and a 5th arm is added as a control group. Figure 1 illustrates the trial design and Figure 2 summarizes the timeline of the trial consisting of an approximate 12-18 months enrolment period, and 12 months of follow-up. The trial adheres to the Consolidated Standards of Reporting Trials (CONSORT) guidelines for conducting and reporting clinical trials, as extended to non-pharmacologic interventions. Two hundred (200)

participants with Mild Cognitive Impairment (MCI), aged 60 and older will be enrolled and randomized into one of five arms.

Arm 1: **multimodal exercises + cognitive training + Vitamin D**

Arm 2: **multimodal exercises + cognitive training + placebo D**

Arm 3: **multimodal exercises+ control cognitive training + Vitamin D**

Arm 4: **multimodal exercises + control cognitive training+ placebo D;**

Arm 5: tone-stretching exercises + control cognitive training+ placebo D.

Note: in **bold** are the active interventions. Arm 5 is the arm with pure control interventions.

Figure 1 shows the flow chart of the trial. E: multimodal exercises; **CT**: cognitive training; **cE**: control tone-stretching exercises; and **cCT**: control cognitive training.

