5. Pre-existing or current active participation in physical activity program involving aerobic or resistance training regimen in previous 6 months.
6. Taking Cognitive enhancers, Neuroleptics, Anticholinergics, or Vitamin D in doses more than 1000IU/day or equivalent.
7. Known hypercalcemia and/or disorder that is cause of hypercalcemia (e.g. hyperparathyroidism/ Paget's disease/ Sarcoidosis).
8. Known renal/kidney insufficiency.
9. Uncontrolled hypertension.
10. Uncontrolled diabetes.

5.3 SAMPLE SIZE:

Sample size calculation is based on changes in our main primary outcome: stabilization/improvement in cognition as measured using the **Alzheimer Disease Assessment Scale Cognitive Plus** (ADAS-Cog Plus). We expect a change of three (3) points on the ADAS-Cog Plus scores, a value that is considered clinically significant, and it is similar in magnitude to the improvements seen in positive pharmacological clinical trials in dementia.[26] Two previous studies testing the effect of exercises on cognition in 200 MCI participants shown a mean score of 6-7 and a standard deviation of 3 in the ADAS-Cog.[24,31] Based on these data and assuming a mean change of 3 points in the ADAS-Cog, 34 participants per arm are required to have 80% power to detect a change of three points or more on the ADAS-Cog with a 2-tailed α error of 5%, adjusted for 10 potential pairwise comparisons. We estimate a worst case scenario of 15% of dropout rate during the 20 weeks of follow up to the main endpoint. Therefore, we will aim to recruit 40 per arm for a total of 200 participants.

Sample size estimates per group for the primary outcome: change in ADAS-Cog Plus

	Type I error=0.05	Type I error=0.01	Type I error=0.001
Power=80%	34	50	59
Power=90%	51	54	70
Power=99%	68	82	102

Reference: Independent Groups - Machin D, Campbell M, Fayers, P, Pinol A (1997) Sample Size Tables for Clinical Studies Second Ed. Blackwell Science ISBN 0-86542-870-0 p. 24-25

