6.1.3 VITAMIN D SUPPLEMENTATION

Participants will receive Vitamin D supplementation (1 tablet of 10,000IU of Vitamin D₃) or matching placebo three times per week in order to reach a weekly cumulative dose of 30,000 IU per week (equivalent of 4,258 IU daily). The vitamin D capsules will be provided by the Research Coordinator

(RC) in vials at baseline assessment and every four weeks to complete 5 vials during the training period. Vials will be returned by the participants to the RC at the end of each 4 weeks block. Rationale and bio-safety of the dose: The dose of 10,000 IU/day is currently approved by Health Canada as a supplementation for elderly patients. Heaney et al. have administered doses of 30,000 IU/day Vitamin D₃ to adult men for five months, with no significant changes in serum calcium concentrations or adverse reactions.[35-37] A comprehensive review of toxic effects of vitamin D found that the lowest level at which an adverse effect was observed was a serum calcidiol concentration of 200 nmol/l, corresponding to a daily intake of 40,000 IU. Therefore, three weekly doses of 10,000IU have a 9-fold weekly margin of safety of the established safe dose.

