243 exercise and vitamin D intervention (arm 1 and 3) and pooling the intervention arms
244 providing exercise intervention but not vitamin D (arm 2 and 4). A new independent
245 variable will be created to represent addition of vitamin D: both aerobic-resistance
246 exercise and vitamin D intervention (pooled arm 1 and 3) and aerobic-resistance
247 exercise but no vitamin D intervention (pooled arm 2 and 4). The linear mixed model will
248 be repeated using this new independent variable and the two pooled arms will be
249 compared. This will allow to explore whether adding vitamin D to aerobic-resistance
250 exercise improve the outcome compared to the aerobic-resistance exercise. If a
251 significant difference is observed, the two pooled arms will be compared to the control
252 arm (arm 5) to assess the main effect.

253 10.2.4 Effect of multidomain intervention

254 The objective 4 (effect of multi-domain intervention (aerobic-resistance exercise +
255 cognitive training + Vitamin D supplement) on cognitive function) will be assessed using
256 the time x intervention arm interaction fitted in the linear mixed model in section 10.2.
257 The interaction term between time x intervention arm 1 will represents the effect of
258 multidomain intervention (arm 1) compared to the control (arm 5).

259 **10.2.5 Long-term effect: From Baseline and Post-intervention to Follow up**

260 The long-term intervention effect from baseline and post-intervention to follow-up
261 (Month 12) will be assessed using the linear mixed model. Time will be used as a
262 categorical variable (Baseline, Month 6, and Month 12). Individuals with incomplete
263 follow up assessments will still be included in the linear mixed model.

264 **10.2.6 Post-hoc analyses**

265 ADAS-Cog-Plus is a construction proposed originally by Skinner et al.⁹, adding extra
266 tests for executive function and verbal fluency to increase sensitivity to detect
267 progression from MCI to dementia. Post hoc analyses will be performed to explore the
268 effect of intervention on ADAS-Cog-Plus scores by adding individual Plus items, one by
269 one, to ADAS-Cog-13.

270 **10.3 Secondary Outcomes Analyses**

271 The secondary analysis will be performed in an intention-to-treat population and a per-
272 protocol population. The details of the statistical analysis plan for secondary outcomes
273 are not included in this analysis plan as the secondary outcome analyses will not be

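### The closing sentence of protocol 9.1, on giving vitamin D analogues concurrently, is inconsistent with the hypercalcaemia safeguards and the placebo-D design and must be reconciled with them

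*Combined protocol and SAP*

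**What the plan says.** The last line of protocol 9.1 reads "Different Vitamin D analogues should be administered concurrently". The entries before it are cautions or interaction notices. One of them states "Vitamin D should be used with caution in patients on digoxin as hypercalcemia (which may result with Vitamin D use) may precipitate cardiac arrhythmias", and the thiazide entry also warns of hypercalcaemia.

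Other parts of the plan bear on the same matter:

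- Protocol 9.2: "Higher doses of Vitamin D may lead to hypervitaminosis D manifested by hypercalcemia and its sequelae". The section goes on to describe stopping vitamin D3 as part of managing intoxication.
- Protocol 9.3 lists "hypercalcaemia and/or hypermagnesemia" among the developments for which a participant may be withdrawn or discontinued.
- Protocol 5.2, exclusion 6: "Taking Cognitive enhancers, Neuroleptics, Anticholinergics, or Vitamin D in doses more than 1000IU/day or equivalent".
- Protocol 6.1.3 sets the study supplement: one 10,000 IU tablet or matching placebo, "three times per week in order to reach a weekly cumulative dose of 30,000 IU per week (equivalent of 4,258 IU daily".
- Protocol section 3 gives placebo D to arms 2, 4 and 5. The control arm is defined as "Arm 5: tone-stretching exercises + control cognitive training+ placebo D".
- SAP 10.2.3 compares pooled arms 1 and 3 with a group described as "exercise but no vitamin D intervention (pooled arm 2 and 4".

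**The concern.** Section 9.1 is where site staff look to learn what may be taken alongside the study supplement. A sentence there that says vitamin D analogues should be given together reads as a rule of conduct, not as background. It is complete and grammatical, so neither redaction nor broken text extraction explains it.

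Two things are at stake. The first is safety: further vitamin D, with no stated limit, would come on top of the study dose in arms 1 and 3, in a protocol that treats hypercalcaemia as a reason to stop. The second is the vitamin D question itself, Objective 3 in SAP section 2. Its estimate is interpretable as the effect of adding vitamin D only if the comparator arms do not receive it through the trial. Objective 4 (arm 1 versus arm 5) also relies on arm 5 being on placebo D.

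**Working it through.** No power or error-rate figure depends on this sentence. The check is mainly a comparison of texts, with a little arithmetic on dose and arm size.

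**Plan's own dose figure.** 3 × 10,000 = 30,000 IU per week, as stated in 6.1.3. Per day this is 30,000 / 7 = 4,286 IU, against 4,258 IU printed. The difference of about 28 IU does not affect this point.

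**The sentence against each related provision, strongest conflict first.**

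1. *Placebo D and the SAP comparator (protocol section 3; SAP 10.2.3).* Arms 2, 4 and 5 are assigned placebo D, and arms 2 and 4 form the no-vitamin-D side of the contrast. Giving a vitamin D analogue in those arms under a protocol rule would contradict that description. This is a direct conflict.
2. *Hypercalcaemia provisions (9.1 itself, 9.2, 9.3).* These treat hypercalcaemia as a hazard of vitamin D, describe stopping vitamin D3 when intoxication occurs, and allow discontinuation if hypercalcaemia develops. An unlimited direction to combine analogues runs against all three. This is a clear inconsistency, although 9.2 is a risk statement and prohibits nothing.
3. *Exclusion 6 (5.2).* This excludes people who take more than 1,000 IU/day at entry, so it admits those who take less. It sets no limit during the trial. An uncapped direction fits poorly with the purpose of such a limit, but the two can both be obeyed. This is the weakest conflict.

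**Numbers potentially affected.** At 40 per arm (protocol 5.3), arms 1 and 3 hold 2 × 40 = 80 participants and arms 2, 4 and 5 hold 3 × 40 = 120. These are planned arm sizes. They would be the numbers affected only if every site gave an analogue to every participant.

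**Effect on the contrast.** Let a₁ be the average non-study vitamin D in arms 1+3 and a₀ that in arms 2+4, in IU per week of vitamin D3 equivalent. The exposure difference is then 30,000 + a₁ − a₀.

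- If a₁ = a₀, the difference stays at 30,000 IU per week. As an illustration, assume everyone takes the largest amount admitted at entry: 7 × 1,000 = 7,000 IU per week, giving 37,000 against 7,000. The dose gap is intact, but the comparison is now of more with less vitamin D, not of some with none.
- If a₀ > a₁, the difference falls below 30,000. If a₁ > a₀, it rises above.

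The documents give neither a₁ nor a₀, and the sentence states no dose, so the change cannot be calculated.

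**The case against.** The best reply is that the sentence is a drafting slip with no practical force. It appears in a list of cautions about drugs participants may already be taking, and it names no product, dose, schedule, arm or supply route. What is given is fixed in 6.1, 6.1.3 and 6.2.2, and the research pharmacy assigns kits by randomisation list (7.2.1). No section provides for supplying any other vitamin D product. Known hypercalcaemia is excluded at entry, and hypercalcaemia that develops can lead to discontinuation.

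Much of this stands. A slip is plausible, and the supply arrangements make it unlikely that all participants were given an analogue. But the documents do not confirm a slip, and a site cannot amend the text on its own authority. The hypercalcaemia provisions limit the consequences of extra exposure; they do not settle what the sentence permits.

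The reply also disposes of three stronger readings that a reader might infer:

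- *That sites cannot comply with both 9.1 and exclusion 6.* Not supported, because exclusion 6 governs entry only.
- *That 80 participants received more than the study amount and 120 were not on a true placebo.* Not supported. Nothing shows that any site acted on the sentence.
- *That the Objective 3 comparison is invalid.* Not supported. Lower-dose vitamin D use at entry was already admitted in every arm, so the placebo-D arms were never guaranteed to be free of vitamin D, and equal use across arms would leave the dose gap unchanged.

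**Conclusion.** The concern holds as an internal inconsistency. One unqualified sentence in the conduct text contradicts the placebo-D assignment and the SAP comparator, and runs against the plan's hypercalcaemia provisions. Its tension with exclusion 6 is real but secondary.

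The possible consequences are added vitamin D exposure and a blurred arms 1+3 versus 2+4 contrast. Both depend on sites having acted on the sentence, which the documents neither show nor rule out. The size of any effect is unknown, and the 80 and 120 are a ceiling that assumes universal use. This conclusion rests on the literal wording and on the absence of any limiting text. It takes no position on which clinical rule the sponsor intended.

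**What to change.** Reconcile the last sentence of protocol 9.1 with section 3, exclusion 6 in 5.2, sections 9.2 and 9.3, and SAP 10.2.3, so that they state one consistent position on non-study vitamin D during the trial. Send the reconciled text to all five sites. The sponsor decides its clinical content.

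The SAP is dated September 2022, so dosing may already be complete, although the documents do not say so. If it is, record the reconciliation and report non-study vitamin D use by arm. The sources already exist: the clinical-medical questionnaire records chronic medications at baseline, 6 and 12 months (7.6.1), the follow-up call asks about medication changes (6.1), and serum vitamin D is measured before and after the intervention (7.6.3; SAP 9.5). If the questionnaire did not capture supplement name or dose, the report should say so. Serum change in arms 2, 4 and 5 would then be the main indirect evidence.

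The cost is a short amendment with research ethics board approval (11.1) and a site notice or, after dosing, a documented clarification and one descriptive table. Sample size and the primary model are unchanged.
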